### **Randomization**

Multiple pharmacies are involved in participant enrollment--therefore, once informed written consent is obtained from the patient, the patients will be randomised by stratified randomization using a blocking factor to assign participants to either intervention or usual care groups.

Each participant will be assigned a unique identifier number and group allocation for the duration of their participation in the study--this unique identifier and allocation will also be communicated to and recorded by the pharmacy partner in the participant's patient profile to ensure consistency of the degree of pharmacist interventions described by the group the participant is allocated to.

The participant will be sent a secured electronic link (to the contact number or email they provided in the written consent form) that will include the participant's unique identifier and group allocation and the electronic version of the PHQ-9/GAD-7 questionnaire tool to complete and submit electronically. If the participant is unable to provide a means for the electronic link to be sent, the questionnaire tool can be completed with the pharmacist partner in person prior to their scheduled in-person/telehealth pharmacist meetings.

The study data (i.e. the participant's submitted electronic questionnaire tool results) will be sent directly to a centralised and secured website/database to ensure allocation concealment for the investigational team.

The participant questionnaire scores are available to the pharmacist partner via a secured electronic website/database prior to their scheduled in-person/telehealth meeting with the pharmacist partner.

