## **Outcomes:**

### **Primary outcomes:**

The primary outcome is the mean score difference in PHQ-9 and GAD-7 scores from baseline to end of study participation, between the intervention and standard pharmacist care groups.

- Both PHQ-9 and GAD-7 are validated tools for measuring major depressive disorder and generalised anxiety, respectively, in the primary care setting. They are brief and can be self-administered, with similar results yielded with health care provider administered reports. These are desirable given the time restraints and competing demands we anticipate for community pharmacist partners participating in the study(11, 12).
- PHQ-9 scores reflect depression severity; Ranges from 0-27 (Scores: 0-4 none/minimal, 5-9 mild, 10-14 moderate, 15-19 moderately severe, 20-27 severe) (13).
- GAD-7 scores reflect anxiety severity; Ranges from 0-21 (Scores: 0-4 none/minimal, 5-9 mild, 10-14 moderate, 15-21 severe) (13)

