### **Sample size and analytical plan:**

#### Sample Size Calculation:

Lindell et al (2018), who evaluated the impact of a psychiatric clinical pharmacists intervention on the change in PHQ-9 and/or GAD questionnaire scores (14), reported a baseline PHQ-9 mean of 15.2 (Standard deviation [SD] of 6.9) and GAD mean of 12.0 (Standard deviation [SD] of 5.8).

Using those reported values and the following assumptions of an 80% power and a 2 sided alpha of 0.05, a sample size of:

- 84 patients (42 in each group) is required to detect a 4.3 point difference in the mean reduction in PHQ-9 scores between the intervention and control group
- 80 patients (40 in each group) are required to detect a 8.3 point difference in the mean reduction in GAD scores between the intervention and control group.

We selected the larger sample size of 84 patients and inflated it by 10%(47 in each group) to account for potential losses to follow-up and withdrawal of consent.

A Data Safety monitoring board will be formed to review adverse events, and data will be sent once recruitment reaches 25% (24 participant) recruitment.

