#### **Analytical Plan:**

All analyses will be conducted on an intention to treat basis. In the case of missing data, a last observation carried forward approach will be used.

Primary outcome will be analysed using ANCOVA, adjusting for all covariates with  $p < 0.25$  between groups

Secondary outcomes will be analysed using ANCOVA, t-test or chi-square test where appropriate, adjusting for all covariates with  $p < 0.25$  between groups.

Trial and Data Management will be done by EPICORE Centre

---

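### The primary ANCOVA picks its covariates by a between-arm test at p<0.25, and nothing guarantees the baseline score or the randomisation strata a place in the model

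*Protocol*

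**What the plan says.** The Analytical Plan gives the primary model in one sentence: "Primary outcome will be analysed using ANCOVA, adjusting for all covariates with" a between-group p-value below 0.25. The next sentence carries the rule over: "Secondary outcomes will be analysed using ANCOVA, t-test or chi-square test where appropriate, adjusting for all covariates with" the same threshold. No candidate covariates are listed and none is named as always included.

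The primary outcome, under Primary outcomes, is the "mean score difference in PHQ-9 and GAD-7 scores from baseline to end of study participation", compared between arms. The Design section makes the patient the unit of randomisation. The Randomization section says "the patients will be randomised by stratified randomization using a blocking factor". It gives enrolment at several pharmacies as the reason, but does not name the stratification factor or say that it enters the analysis.

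**The concern.** After individual randomisation, a baseline difference between arms is chance. A between-arm p-value therefore says nothing about whether a covariate predicts month-6 symptoms. A 0.25 screen admits an unstratified covariate with probability 0.25 whether or not it is prognostic, and discards a strong predictor that happens to be balanced.

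Two sets of variables matter most.

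- **Baseline score.** It is the natural covariate for a from-baseline outcome, yet on the literal wording it enters only when it is imbalanced.
- **Stratification factors.** Stratified, blocked randomisation balances them by design, so their between-arm p-values will usually be large and the screen will tend to exclude them.

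At stake are power, correctly sized confidence intervals, and a primary model that can be known before the data are seen. In addition, the outcomes listed under Secondary outcomes are proportions or percentages. The plan would use a chi-square test adjusted for covariates, which that test cannot do. Nor can a t-test.

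**Working it through.** **Inputs from the Sample Size Calculation.** "assumptions of an 80% power and a 2 sided alpha of 0.05"; "baseline PHQ-9 mean of 15.2 (Standard deviation [SD] of 6.9"; a sample to "detect a 4.3 point difference in the mean reduction in PHQ-9 scores between the intervention and control group"; 42 evaluable patients per arm.

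**Assumptions (not in the protocol).** Pre-post correlation r = 0.3, 0.5 or 0.7; normal scores with SD 6.9 at both times; baseline score as the only candidate covariate.

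**Step 1: reproduce the planned size.**
n per arm = 2(1.96 + 0.8416)² × 6.9² / 4.3² = 2 × 7.849 × 47.61 / 18.49 = 40.4, rounded up to 41. With the noncentral t distribution, power is 79.6% at 41 per arm and 80.6% at 42. So 84 is the figure for an unadjusted two-sample t-test with SD 6.9. Allowing for 10% loss, 42 / 0.9 = 46.7, rounded up to 47, which matches the protocol.

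**Step 2: residual SD with and without baseline.**
Unadjusted change: 6.9 × √(2(1 − r)). With baseline in the model: 6.9 × √(1 − r²).

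| r | Change, unadjusted | Baseline in model |
|---|---|---|
| 0.3 | 8.16 | 6.58 |
| 0.5 | 6.90 | 5.98 |
| 0.7 | 5.35 | 4.93 |

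The unadjusted final score has SD 6.9 throughout.

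**Step 3: simulate the rule.** There were 100,000 trials per setting, with a true difference of 0 (type I error) or 4.3 (power). Under the rule, baseline is in the model only if its between-arm t-test gives p<0.25. It entered in 24.9 to 25.2% of trials, so it was omitted in about 75%.

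| Outcome, r | Power, no adjustment | Power, rule | Power, baseline always in | Loss (points) | Type I error, rule | 95% CI coverage, rule |
|---|---|---|---|---|---|---|
| Change, 0.3 | 66.5% | 71.8% | 83.5% | 11.7 | 3.2% | 96.8% |
| Change, 0.5 | 80.5% | 84.1% | 90.0% | 5.9 | 3.8% | 96.2% |
| Change, 0.7 | 95.3% | 96.4% | 97.5% | 1.1 | 4.2% | 95.8% |
| Final, 0.3 | 80.7% | 81.6% | 83.6% | 2.0 | 4.5% | 95.5% |
| Final, 0.5 | 80.6% | 84.2% | 89.9% | 5.7 | 3.7% | 96.3% |
| Final, 0.7 | 80.7% | 87.9% | 97.5% | 9.6 | 2.6% | 97.4% |

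With baseline always in the model, type I error is 4.9 to 5.1%.

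**Step 4: why the rule is conservative.** Baseline is omitted exactly in the trials where the arms are well balanced on it. In those trials the estimate varies less than the unadjusted standard error allows for. For the change score at r = 0.3, the estimate's actual SD under the rule is 1.544, while the mean reported standard error is 1.697. Type I error within the trials that omit baseline is 2.6% there.

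**The case against.** **ANCOVA may already imply baseline.** The plan names ANCOVA without condition, for a from-baseline outcome. If nothing passed the screen, the literal rule would leave no ANCOVA at all. It is reasonable to think that the authors take the baseline score as given and screen only additional covariates. This stands as a possible intention, and on that reading the losses above do not arise. But the sentence applies the screen to all covariates and exempts none. The 75% is a consequence of the wording, not an established fact about how the trial will be analysed.

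**A reader might infer a risk of false positives.** The calculations show the opposite: type I error is below 5% in every setting.

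**A reader might infer that the rule drags the trial below its planned 80%.** The comparison is with a better analysis, not with the plan's unadjusted calculation, and the rule beats no adjustment in all six settings. Among these settings power is below 80% only for the change score at r = 0.3 (71.8%). That shortfall comes largely from a change-score SD of 8.16 where the sample size used 6.9; unadjusted power there is 66.5%. What can be laid at the rule's door is the failure to recover the 83.5% that fixed adjustment gives.

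**A reader might count the items in Appendix 5 and predict how many would enter by chance.** That appendix describes information gathered in standard pharmacist care. It is not a list of candidate covariates, so no such number can be supported.

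**The detail could be left to a SAP.** That would answer an omission. Here the protocol itself fixes a selection rule, and a SAP that follows it inherits the rule.

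**On the secondary outcomes,** the qualifier in the sentence governs which test is chosen. It does not make an adjusted chi-square test or t-test possible.

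**Conclusion.** The concern holds in a limited form. Selecting covariates by between-arm p<0.25 is unsound in a randomised trial whatever is decided about baseline, and the protocol secures neither the baseline score nor the strata a place in the model.

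On the literal reading, the cost is conservative inference (type I error 2.6 to 4.5%, coverage 95.5 to 97.4%) and a power loss against fixed adjustment of 1 to 12 points for the change score, or 2 to 10 points for the final score. The size rests on an assumed correlation of 0.3 to 0.7, equal SDs and full follow-up of 42 per arm. For the change score the loss shrinks as the correlation rises; for the final score it grows.

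The effect of omitting the strata was not quantified, because the protocol does not name them. If they are prognostic, leaving them out also makes standard errors too large. The statement about secondary outcomes cannot be carried out as written.

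**What to change.** Delete the p<0.25 screen from both sentences of the Analytical Plan and replace it with the following.

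- **Primary:** for PHQ-9 and GAD-7 separately, ANCOVA of the end-of-study score on arm, the baseline value of the same scale, and the stratification factor(s) used at randomisation, which should be named. Using the change score instead gives the same treatment estimate once baseline is in the model. Any further covariate is named in advance; none is chosen by a between-arm test.
- **Binary secondary outcomes:** logistic regression with the same prespecified covariates.

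If baseline was always meant to be included, the text should say so outright; the screen for other covariates should still go.

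The cost is about two sentences and no new data, since the baseline questionnaire is already collected in both arms. The change should be made before outcome data are examined.

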### **Secondary outcomes:**

- Difference in the clinical improvement rates (proportions of participants achieving clinically significant treatment response) between the pharmacist intervention and standard pharmacist care groups from baseline until the end of the study period, using the PHQ-9 and GAD-7 score.
  - For our study, clinically significant treatment response for the PHQ-9 is defined as a reduction in PHQ-9 score by at least 50% from baseline; adequate treatment response for the GAD-7 is defined as a drop in the GAD-7 score by at least 50% from baseline.
- Difference in the proportion of participants with MDD to achieve PHQ-9 score <5 (i.e. remission/no depression) between the pharmacist intervention and standard pharmacist care groups
- Difference in the proportion of participants with GAD to achieve GAD-7 score <5 (i.e. remission/no anxiety) between the pharmacist intervention and standard pharmacist care groups
- Percentage difference in self-reported safety concerns disclosed by participant to pharmacist partner anytime during the study period, between the pharmacist intervention and standard pharmacist care groups:
  - Adverse medication effects (e.g. dizziness, GI intolerance, bleeding, palpitations suggestive of prolonged QTc interval, etc.)

- Suicidal ideation, attempt at suicide
  - Causing withdrawal from study
- 

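### The protocol promises covariate-adjusted secondary analyses but names no model that suits adjusted comparisons of proportions

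*Protocol*

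**What the plan says.** The Analytical Plan gives one sentence to each tier of outcome. For the primary: "Primary outcome will be analysed using ANCOVA, adjusting for all covariates with" a between-group p-value below 0.25. For the secondary: "Secondary outcomes will be analysed using ANCOVA, t-test or chi-square test where appropriate, adjusting for all covariates with" the same cut-off. The second sentence attaches the adjustment to all three methods that it lists.

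The Secondary outcomes section lists four kinds of outcome:

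- Response on the PHQ-9 and GAD-7, meaning a fall of at least half from baseline, compared as "proportions of participants achieving clinically significant treatment response".
- PHQ-9 remission: "Difference in the proportion of participants with MDD to achieve PHQ-9 score <5".
- GAD-7 remission: "Difference in the proportion of participants with GAD to achieve GAD-7 score <5".
- Safety: "Percentage difference in self-reported safety concerns disclosed by participant to pharmacist partner anytime during the study period".

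No logistic or other binary regression, and no stratified chi-square test, is named anywhere in the protocol.

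**The concern.** Of the three named methods, the chi-square test is the one designed to compare proportions. It uses only the two-by-two table of group by outcome, so no covariate can enter it. The two-sample t-test has no place for one either. ANCOVA does take covariates, but it is normally a model for a continuous score, and the protocol does not say that it is meant for yes/no outcomes. The promise of adjustment therefore does not fit the test that suits the listed outcomes.

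This is separate from how covariates are selected: a fixed covariate list could not be used in a chi-square test either.

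Two statisticians following the same sentence could report different results for remission, one from an unadjusted chi-square test and one from an adjusted model of their own choosing. Baseline severity is likely to predict whether a participant ends below 5, so leaving it out also gives up some precision in a small trial.

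**Working it through.** **1. The plan's own sample size.** The inputs, from Sample Size Calculation, are the "assumptions of an 80% power and a 2 sided alpha of 0.05", an SD of 6.9 ("reported a baseline PHQ-9 mean of 15.2 (Standard deviation [SD] of 6.9") and a difference of 4.3 points.

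- Normal approximation: n per group = 2 × (1.960 + 0.842)² × 6.9² / 4.3² = 40.4, so 41.
- t-based calculation: 41.4, so 42, the plan's figure.
- With 10% loss: 42 / 0.9 = 46.7, so 47, also the plan's figure.

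The point disputes none of these numbers; 42 per group and SD 6.9 are used below.

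**2. Methods against outcomes.**

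| Named method | Takes covariates? | Suits a difference in proportions? |
|---|---|---|
| ANCOVA | Yes | Only as a linear model on a 0/1 outcome, which is not stated |
| t-test | No | No |
| Chi-square test | No | Yes |

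No row combines covariates with a stated use for proportions.

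**3. The choice can change a result.** This example uses assumed counts: 13 of 42 responders against 21 of 42. The chi-square statistic is 84 × (13 × 21 − 29 × 21)² / (34 × 50 × 42 × 42) = 3.16, p = 0.075, whatever the baseline data. Logistic models on the same counts, each adjusted for a different simulated covariate, gave odds ratios of 2.32, 2.29 and 2.78, with p = 0.068, 0.072 and 0.046. The last covariate was simulated to be related to the outcome. This shows only that the choice can cross 0.05; it does not predict this trial.

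**4. Effect of a chance baseline imbalance on PHQ-9 remission.**

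- Standard error of the baseline difference: 6.9 × √(2/42) = 1.51 points.
- Difference giving p = 0.25: 1.15 × 1.51 = 1.73 points.
- Assumed, because the protocol gives no month 6 values: mean 9, SD 6, correlation with baseline 0.4, normal scores, no treatment effect. Below 5 is taken as below 4.5.
- Slope on baseline: 0.4 × 6 / 6.9 = 0.348. An imbalance of 1.5 points moves the month 6 mean by 0.52.
- Remission without the shift: Φ((4.5 − 9)/6) = Φ(−0.75) = 22.7%.
- Remission with it: Φ((4.5 − 9 − 0.52)/6) = Φ(−0.837) = 20.1%. The shift is 2.5 percentage points.
- At 1.73 points the shift is 2.9 percentage points.

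With month 6 means of 7, 9 and 11, SDs of 5.5 and 6, and correlations of 0.3, 0.4 and 0.6, the same formula gives 1.2 to 4.6 percentage points at one standard error and 1.4 to 5.3 at the p = 0.25 cut-off.

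**5. Setting that against sampling error.** At 22.7% remission, the standard error of the difference is √(2 × 0.227 × 0.773 / 42) = 9.1 percentage points. The one-standard-error shift is 2.5 / 9.1 = 0.28 of it. To a first approximation, baseline imbalance makes up 0.28² = 8% of the variance, so adjusting for it would bring the standard error from 9.1 to about 9.1 × √0.92 = 8.8. Over the same grid the ratio runs from 0.18 to 0.45, which is 3% to 20% of the variance.

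**The case against.** The strongest reply is that the adjusted analysis is possible with what is named. ANCOVA fitted to a 0/1 outcome is a linear model that returns an adjusted risk difference, which is the quantity the Secondary outcomes section asks for. A stratified chi-square test can also take categorical factors. This stands against any claim that adjustment is impossible. It does not rescue the sentence, because the protocol specifies neither route and lists the plain chi-square test alongside.

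A second reply is that the phrase leaving the choice of test open limits adjustment to outcomes where ANCOVA is used. The secondary objectives mention functional impairment, satisfaction and quality of life, some of which may be continuous, and ANCOVA would suit those. But they are not in the Secondary outcomes list. On this reading the adjustment clause would apply to none of the outcomes that are.

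A third reply is that choosing a binary model is ordinary work for a statistical analysis plan. That is fair as far as it goes: such a plan may exist and may settle the model before the data are seen, so it cannot be asserted that the choice will be made afterwards. But the protocol is not silent here. It pairs adjustment with tests that cannot adjust, and any later plan would have to depart from one or the other.

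The size is also modest and rests on assumed inputs. The 42 per group is an upper figure for PHQ-9 remission in a fully evaluable sample of 84, since that outcome covers participants with MDD only and the trial admits people with GAD alone. A smaller number enlarges both the shift and the standard error in the same proportion, so their ratio is unchanged.

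**Conclusion.** The inconsistency is real. As worded, the plan ties covariate adjustment to two tests that take no covariates, and for the proportions it lists it names no binary model that would deliver it. The wording should be corrected, but the consequence is limited: these are secondary outcomes, and the primary analysis by ANCOVA is not touched by this point.

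A reader might infer that the adjusted analysis cannot be carried out at all. That holds only for the t-test and chi-square test as named. A reader might also infer that an unadjusted chi-square test would be biased or give too many false positives. It would not: under randomisation, chance imbalance is already part of that test's sampling error. The loss is precision, roughly 8% of the variance under the central assumptions and 3% to 20% across the range, together with an analysis choice that the protocol leaves open.

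The shift of about 2.5 percentage points (about 1 to 5 across the assumptions and imbalances examined) rests on month 6 values that are not in the protocol, and should be read beside the standard error of about 9 points.

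**What to change.** State that response and remission at month 6 are analysed with a prespecified regression for binary outcomes containing treatment and the corresponding baseline score (PHQ-9 for the PHQ-9 outcomes, GAD-7 for the GAD-7 outcomes). Logistic regression with standardisation to an adjusted risk difference is one suitable choice among several.

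The Randomization section says that allocation is stratified but does not name the factor. Name it, and include it in the model only if it has few enough levels for about 42 to 47 participants per group. If the factor is pharmacy and there are many sites, the model could become sparse.

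For sparse safety events, state an unadjusted exact or chi-square test and remove the adjustment wording for them. If any continuous secondary outcome is intended, list it and keep ANCOVA for it.

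The cost is a change of wording. Both questionnaires are already scheduled at enrolment and month 6 in both groups, so no new data or participants are needed.

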**Feasibility:**

## Remuneration:

Participant Pharmacists will submit to Alberta Health for remuneration of baseline (Comprehensive Annual Care Plan [CACP] or Standard Medication Management Assessment [SMMA]) and follow-up visits, based on eligibility as per Ministerial Order 614/2018 (15, 16). In addition, prescription services that include: initial access prescribing, prescribing to adapt, management of ongoing therapy, and prescribing to renew medication therapy--will also be submitted for remuneration.

**Training for Pharmacist Partners:**

## i) Training and support material:

These will be developed by the research team in close collaboration with psychiatric pharmacist consultants and disseminated via online telehealth platform and/or in person.

- Recordings of these meetings will be made available
- Additional materials will be developed/acquired from major organisations:
  - Canadian Task Force for Preventative Health Care (CTFPHC)
  - Canadian Pharmacist Association (CPHA)
  - Canadian Network for Mood and Anxiety Treatments (CANMAT)
  - Centre for Addiction and Mental Health (CAMH)

Training and support materials will include the following topics:

- Case finding
- Major Depressive Disorder and Generalised Anxiety disorder
  - PHQ9 and GAD7 scoring
  - Clinical assessment and monitoring for patients with depression and anxiety
- Managing Adverse Effects
- Switching medications
- Alberta Health Services Access Mental Health “Know Your Options” brochure
- Preparing CACP and SMMA for remuneration
- CANMAT 2016 guideline for the management of adults with MDD (including treatment, adjustment, and add-on algorithm)
- CANMAT 2014 guideline for the management of anxiety (focusing on GAD treatment)

